## 2. LAY SUMMARY

Over 2 million people in the UK suffer from cardiac arrhythmias (heart rhythm problems). The most common type of arrhythmia is atrial fibrillation (AF), the heart beats irregularly and usually rapidly. Other arrhythmias may cause the heart to beat slower or faster than normal. Heart rhythm problems can range from being an inconvenience to a serious health problem. Although patients may complain of palpitations, dizziness, chest discomfort or even shortness of breath, many don't experience any symptoms.

An electrocardiogram (ECG) uses sensors placed on the skin to record the heart's electrical activity. A 12-lead ECG uses 10 sensors (one in each limb and 6 on the chest) and is the gold-standard (best available test) to detect any abnormal heart rhythm disturbances. However, some arrhythmias, such as AF, may be short and unpredictable, and may not be captured when a 12-lead ECG is undertaken. Therefore, a small (non-intrusive) device that continuously tracks your heartbeat and record a 1-lead ECG could make the diagnosis of cardiac arrhythmias much quicker and easier.

Accessories such as watches, bands or rings — referred to as wearable devices — have extremely good sensors that measure pulse rate by detecting small changes in skin colour during each heartbeat. More advanced wearable devices, such as the Apple Watch and the Skylab CART-I ring, can also perform a 1-lead ECG which is sent directly to your doctor.

These commercially available wearable devices do not go through the same rigorous testing as hospital equipment. Robust tests are essential before they are used in patients as an 'abnormal' finding may not represent a true heart rhythm problem but may lead to significant anxiety and trigger unnecessary tests or treatments, which can be harmful.

The purpose of this study is to test how well two commonly used innovative wearable devices — the SkyLabs CART-I ring and the Apple Watch — detect different cardiac arrhythmias. We plan to recruit 500 patients attending Cardiology Departments in several hospitals in the UK and will have a 12-lead ECG as part of their care. Participants will first have a simultaneous 12-lead ECG with a 1-lead ECG from one of the two wearable devices. This will be followed by a second (extra) 12-lead ECG with a 1-lead ECG from the remaining wearable device. Therefore, in addition to their usual 12-lead ECG, participants will have one extra 12-lead ECG and two extra 1-lead ECGs. No extra follow-up visits are required. At the end of the study, we will compare interpretation by heart rhythm specialists of the 1-lead ECGs recorded by the wearable devices and the 12-lead ECG.

### 3. SYNOPSIS

Trial Title	Diagnostic accuracy of WEARable TECHnology single-lead ECG in detecting cardiac arrhythmias: WEAR-TECH ECG		
Internal ref. no. (or short title)	WEAR-TECH ECG		
Trial registration	Intended register – Clinicaltrials.gov		
Sponsor	Oxford University Hospitals NHS Foundation Trust		
Funder	Abbott Educational Grant/CRM research Hub fund/ SkyLabs		
Clinical Phase	Observational study		
Trial Design	Prospective multicenter observational study.		
Trial Participants	Male and female participants who are 18 or older.		
Sample Size	500 participants		
Planned Trial Period	12 months		
Planned Recruitment period	9 months		
	Objectives	Outcome Measures	Timepoint(s)
Primary	Compare the accuracy of physician rhythm interpretation of 1-lead ECG generated by SkyLabs CART-I ring and Apple Watch versus 12-lead ECG (gold-standard)	Sensitivity, specificity, positive and negative predictive value of the SkyLabs CART-I ring and Apple Watch 1-lead ECGs interpretation for different cardiac arrhythmias compared with a 12-lead ECG (gold-standard)	At the time of ECG acquisition
Secondary	1. Compare the accuracy of automatic AF detection of the SkyLabs CART-I Ring and Apple Watch compared to a cardiologist interpretation of a 12-lead ECG (gold-standard)	1. Sensitivity, specificity, positive and negative predictive value of the AF detection algorithm of the Skylab CART-I ring and Apple Watch compared to a 12-lead ECG (gold-standard)	At the time of ECG acquisition

	
2. Compare the accuracy of ECG interval measurement for the SkyLabs CART-I Ring and Apple Watch to a 12-lead ECG (gold-standard)
 
3. Compare the accuracy of heart rate detection of the SkyLabs CART-I ring and Apple Watch 1-lead ECG to a 30-second 12-lead ECG
 
4. Compare the accuracy of rhythm interpretation of SkyLabs CART-I ring 1-lead ECG to combined plethosmography (PPG) signal and 1-lead ECG.
	
2. Level of agreement of measured interval duration between the SkyLabs CART-I ring, Apple Watch 1-lead ECG and a 12-lead ECG.
 
3. Correlation coefficient between the mean heart rate from simultaneous single lead and 12 lead ECG acquisitions
 
4. Compare sensitivity, specificity, positive and negative predictive value of the Skylab CART-I ring if a PPG signal is added
	
Intervention(s)	
Wearable devices
 
 
• SkyLabs CART-I Ring
 
• Apple Watch Series 6
 
		
Comparator	Standard 12-lead Electrocardiogram		

#### 4. ABBREVIATIONS

AE	Adverse event
AF	Atrial fibrillation
AR	Adverse Reaction
AT	Atrial Tachycardia
CI	Chief Investigator
CRF	Case Report Form
ECG	Electrocardiogram
GCP	Good Clinical Practice
GP	General Practitioner
HRA	Health Research Authority
ICM	Implanted Cardiac Monitor
ICF	Informed Consent Form
IRB	Independent Review Board
NHS	National Health Service
OUHFT	Oxford University Hospital NHS Foundation Trust
PI	Principal Investigator
PIS	Participant/ Patient Information Sheet
PPG	Photoplethysmography
R&D	NHS Trust R&D Department
REC	Research Ethics Committee
SAE	Serious Adverse Event

## 5. BACKGROUND AND RATIONALE

Clinical significance: Cardiac arrhythmias are associated with morbidity and economic cost. Rhythm abnormalities increase in frequency with age and approximately 5% of those aged between 65-73 years will have a cardiac arrhythmia but many patients remain unaware. The most prevalent arrhythmias are atrial fibrillation (AF), bradycardia and conduction disorders. A 12-lead electrocardiogram (ECG) is the gold-standard test to identify heart rhythm disorders.

Atrial fibrillation (AF) affects millions of people worldwide; its prevalence is projected to almost double in the next decades. AF is associated with significant morbidity and mortality. AF results in a 5-fold increased risk of ischaemic stroke, accounting for 20-25% of all strokes, which are generally more severe and disabling, more likely to recur and associated with higher-healthcare costs.

Symptoms alone are unreliable in identifying the presence or absence of AF. Early diagnosis allows institution of therapies, such as oral anticoagulation and catheter ablation, which have the potential to reduce arrhythmia burden, improve quality of life and reduce the risk of cardioembolic strokes. Indeed, asymptomatic AF is associated with higher mortality than symptomatic AF. As the prevalence of AF increases, opportunistic screening with pulse palpation followed by a 12-lead ECG is cost-effective and recommend in patients over 65 years of age.

Mobile Health Technology: In the last decade, there has been an exponential growth in mobile health technologies (mHealth) with more than 400 brands and models of wearable activity monitors, including smartwatches, smartbands, rings and vests. Initially designed to track activity and heart rate, many devices now notify users of bradycardia, tachycardia and AF episodes. Most devices use very sensitive optical sensors and photoplethysmography (PPG) to analyse changes in skin colour, light intensity, and absorption to measure heart rate. In addition, advanced proprietary algorithms assess heart rate variability to diagnose AF. PPG technology has several inherent limitations that increase the number of false positive detections of AF, such as noise and artefact from changes in pressure, motion, skin tone and ambient light. More recently, an ECG sensor unit incorporated into smartwatches and rings generates a standard lead I (left arm to right arm vector) ECG which is transmitted to a smartphone app and can be exported in PDF format for further review by physicians. Wearable devices able to record 1-lead ECG can potentially identify other arrhythmias in addition to AF.

The European Society of Cardiology (ESC) recognises the pitfalls of wearable technologies in their recent guidance and recommends caution when interpreting published accuracy data from wearable devices. The guidelines state that AF diagnosis should not be based on PPG signals but can be diagnosed by physician interpretation of a single-lead ECG from a mobile or wearable device. Lastly, it highlights the need for robust validation studies prior to adopting wearable technology and 1-lead ECGs in routine clinical practice.

Undoubtedly, mHealth technology has many potential applications in healthcare, from monitoring cardiovascular risk factors and improving engagement and compliance to screening and monitoring of cardiac arrhythmias. However, the ubiquitous use of mHealth technologies— many without rigorous validation studies — will generate vast amounts of biometric data of uncertain quality and significance and will have several implications for both patients and physicians and for health economics. For patients, an ‘abnormal’ hearth rhythm detection may create significant anxiety and prompt them to take

By placing a finger in the metal portion of the ring, a high quality 30-second single-lead ECG and PPG signal is created in its smartphone app. The automatic analysis will classify the recording as sinus rhythm, atrial fibrillation or uninterpretable.

Rationale: Wearable technologies have the potential to improve the management of patients with atrial fibrillation and other cardiac arrhythmias. Their utility is dependent on having an accurate, reproducible 1-Lead ECG and very sensitive (and reasonably specific) detection of cardiac arrhythmias, including atrial fibrillation. This observational study will investigate the accuracy of two contrasting wearable devices: the Apple Watch Series 6 and the SkyLabs CART-I ring.

**Figure 1.** SkyLabs CART-I ring and Apple Watch Series 6

## 6. OBJECTIVES AND OUTCOME MEASURES

Objectives	Outcome Measures	Timepoint(s) of evaluation of this outcome measure (if applicable)
Primary Objective  Compare the accuracy of physician rhythm interpretation of 1-lead ECG generated by SkyLabs CART-I ring and Apple Watch versus 12-lead ECG (gold-standard)	Sensitivity, specificity, positive and negative predictive value of the SkyLabs CART-I ring and Apple Watch 1-lead ECGs interpretation for different cardiac arrhythmias compared with a 12-lead ECG (gold-standard)	At the time of ECG acquisition
Secondary Objective  1. Compare the accuracy of automatic AF detection of the SkyLabs CART-I Ring and Apple Watch versus a cardiologist interpretation of a 12-lead ECG (gold-standard)  2. Compare the accuracy of ECG interval measurement for the SkyLabs CART-I Ring and Apple Watch to a 12-lead ECG (gold-standard)  3. Compare the accuracy of heart rate detection of the SkyLabs CART-I ring and Apple Watch 1-lead ECG to a 30-second 12-lead ECG  4. Compare the accuracy of rhythm interpretation of SkyLabs CART-I ring 1-lead ECG to combined (plethosmography) PPG signal and 1-lead ECG.	1. Sensitivity, specificity, positive and negative predictive value of the AF detection algorithm of the Skylab CART-I ring and Apple Watch compared to a 12-lead ECG (gold-standard)  2. Level of agreement of measured interval duration between the SkyLabs CART-I ring, Apple Watch 1-lead ECG and a 12-lead ECG.  3. Correlation coefficient between the mean heart rate from simultaneous single lead and 12 lead ECG acquisitions  4. Compare sensitivity, specificity, positive and negative predictive value of the Skylab CART-I ring if a PPG signal is added	At the time of ECG acquisition

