## 7. STUDY DESIGN

This study is a prospective, multicentre, observational study comparing rhythm and heart rate detection of two novel wearable devices — the Skylab CART-I ring and Apple Watch Series 6 — to a 12-lead ECG (gold-standard) for different cardiac rhythm disorders. We will recruit 500 participants attending Cardiology outpatient appointments, procedures or investigations (including the catheterisation laboratory) and inpatients in the cardiology and cardiothoracic wards in three hospitals across the UK. All patients will be due a 12-lead ECG as part of their standard of care.

If participants agree to take part in this study, the research team will provide them with instructions and will demonstrate how to use the wearable devices. Participants will then be asked to perform a simultaneous 30-seconds 12-lead ECG and 1-lead ECG for each wearable device (Skylab CART-I ring or Apple Watch). The order of recordings will be randomly assigned. If the first recording is uninterpretable due to artefact, a second recording will be allowed.

[figure not shown]
The SkyLabs CART-I Ring generates a 30-second 1-lead ECG by placing the participants finger on the rings' metal casing. Similarly, the Apple Watch 1-lead ECG requires the participant to place his/her finger on the metal crown. The 1-lead ECGs will be displayed and saved in the CART-I ring app and Apple Health app of a research iPhone SE, respectively. The smartphone apps will not contain any identifiable data and participants will only be identified by the time stamp of their recordings. The clocks of the Apple Watch, SkyLabs CART-I ring and ECG machine will be synchronised. The 12-lead ECG will also contain a time stamp and the study ID number (site code and participant number), it will then be recorded by using the iPhone SE camera and exported in PDF format for subsequent analysis. The 12-lead ECGs time stamp will also be documented in the CRF. The 12-lead ECGs will be added to the participants medical notes and available to the clinical team. The 1-lead ECGs from the wearable devices will only be available to the research team.

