## 10 STATISTICS AND ANALYSIS

Descriptive statistics are reported as count and percentage for categorical variables and mean and standard deviation for continuous variables.

Adjudication of all anonymised ECGs (12-lead ECGs, 1-lead ECGs from Apple Watch and SkyLabs CART-I ring) will be performed by two Cardiologists blinded to participants' data. Any disagreements will be decided by a third Cardiologist (CI of the study). Following adjudication, the sensitivity, specificity, positive negative predictive values will be calculated for different cardiac rhythm disorders. The level agreement between adjudicators will be calculated using the Cohen's kappa.

ECG waveform analysis and intervals (PR, QRS, QT and RR) will be measured by using callipers to the nearest 0.25 mm. The first three consecutive waveforms will be analysed in each ECG and the intervals averaged. In the 12-lead ECG, it will be to the physician's discretion which lead is chosen to measure the

intervals. To investigate the level of agreement, correlation coefficient and Band-Altman plots will be generated.

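### Secondary objective 3 asks how accurate heart-rate detection is, but its only listed outcome is a correlation coefficient, which does not respond to systematic error

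*Combined protocol and SAP*

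**What the plan says.** Section 6 words secondary objective 3 as "Compare the accuracy of heart rate detection of the SkyLabs CART-I ring and Apple Watch 1-lead ECG to a 30-second 12-lead ECG". The outcome listed against it is "Correlation coefficient between the mean heart rate from simultaneous single lead and 12 lead ECG acquisitions". The Synopsis (Section 3) gives the same pair. The type of coefficient is not named, and no bias, limits of agreement or acceptable error is attached to it.

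Secondary outcome 2, for the ECG intervals, is worded differently: "Level of agreement of measured interval duration between the SkyLabs CART-I ring, Apple Watch 1-lead ECG and a 12-lead ECG".

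Section 10 does not mention mean heart rate or objective 3. Its last paragraph begins "ECG waveform analysis and intervals (PR, QRS, QT and RR) will be measured by using callipers to the nearest 0.25 mm", continues "The first three consecutive waveforms will be analysed in each ECG and the intervals averaged", and ends "To investigate the level of agreement, correlation coefficient and Band-Altman plots will be generated".

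On size, Section 7 says "We will recruit 500 participants attending Cardiology outpatient appointments, procedures or investigations", and each participant is recorded with both devices.

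**The concern.** Accuracy is a question about the size of the error: how far the device reading lies from the simultaneous 12-lead reading, on average and in an individual. Correlation measures how closely the paired readings follow a straight line, whatever the intercept or slope of that line. It also rises with the spread of heart rates in the sample, and this sample mixes outpatients, catheterisation laboratory patients and cardiology inpatients.

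If the outcome is reported as listed, objective 3 could be answered by a high r that says nothing about whether a device reads systematically high or low. The study presents itself as a validation of these devices, and Section 7 names heart rate alongside rhythm in its description of the design. The listed measure should therefore be able to support a statement about heart-rate accuracy.

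**Working it through.** The documents give no target correlation, heart-rate SD, error SD or acceptable bias for objective 3, so there is no figure of the plan's own to reproduce. The SDs and the 10 bpm bias below are assumptions chosen for illustration. Only n = 500 comes from the protocol.

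**1. What r responds to.** Write device = reference + bias + random error, with the error independent of the reference. Then

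r = SD_HR / √(SD_HR² + SD_err²)

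and the 95% limits of agreement are bias ± 1.96 × SD_err. The bias is absent from the first formula and present in the second. For SD_HR 20 and SD_err 5, r = 20/√(400 + 25) = 20/20.62 = 0.970.

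| SD_HR (bpm) | SD_err (bpm) | r, bias 0 | r, bias 10 | Limits, bias 0 | Limits, bias 10 |
|---|---|---|---|---|---|
| 15 | 2 | 0.991 | 0.991 | −3.9 to 3.9 | 6.1 to 13.9 |
| 15 | 5 | 0.949 | 0.949 | −9.8 to 9.8 | 0.2 to 19.8 |
| 20 | 5 | 0.970 | 0.970 | −9.8 to 9.8 | 0.2 to 19.8 |
| 25 | 5 | 0.981 | 0.981 | −9.8 to 9.8 | 0.2 to 19.8 |
| 10 | 5 | 0.894 | 0.894 | −9.8 to 9.8 | 0.2 to 19.8 |
| 20 | 10 | 0.894 | 0.894 | −19.6 to 19.6 | −9.6 to 29.6 |

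The four rows with SD_err 5 have identical limits, yet r runs from 0.894 to 0.981 purely because the patients' heart rates are more or less spread out.

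**2. Proportional error.** For device = k × reference + error, r = k·SD_HR / √(k²·SD_HR² + SD_err²). With k = 1.133, SD_HR 15 and SD_err 2, this is 17.0/√(288.8 + 4) = 0.993, although the device reads 0.133 × 75 = 10 bpm high at a mean of 75 bpm. Without the proportional error r is 0.991.

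**3. Simulation with 500 pairs** (mean 75, SD_HR 15, SD_err 2). r was 0.991 both with no bias and with a 10 bpm bias. The Bland-Altman quantities for the biased device were a mean difference of 10.1 bpm and limits of 6.2 to 14.0 bpm.

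**4. What the RR plot in Section 10 would show.** RR in ms is 60,000 divided by the rate. A 10 bpm error carried in the tracing moves RR from 800 to 706 ms at 75 bpm (94 ms) and from 600 to 545 ms at 100 bpm (55 ms). At an assumed 25 mm/s (40 ms per mm) these are 2.35 mm and 1.36 mm, against a reading step of 0.25 mm. A gross error of this kind would be visible.

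**5. What it would not show.** RR is averaged over three waveforms, whereas objective 3 concerns a 30-second recording. Treating RR intervals as independent, the standard error of a three-interval mean is CV/√3. For an assumed RR coefficient of variation in AF of 0.15 to 0.25, that is 8.7% to 14.4%, or 6.9 to 11.5 bpm at 80 bpm. Part of this would cancel in the device-minus-12-lead difference if the same beats were measured on both tracings, but the protocol does not say that they will be. The protocol also does not say whether the mean heart rate is the value reported by the device or one read from the trace. An error only in a reported value would not appear in calliper-measured RR.

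**6. Precision of the alternative.** With n = 500, the 95% CI half-width for the mean difference is 1.96 × SD_err/√500, which is 0.09 bpm for SD_err 1 and 0.44 bpm for SD_err 5. The existing sample is ample.

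**The case against.** The strongest reply is that Section 10 already covers this. Its agreement sentence is the only place in the statistics section that mentions a correlation coefficient, and outcome 3 is the only outcome defined as one, so the sentence may be meant to serve outcomes 2 and 3 together. Even read narrowly, it gives a Bland-Altman plot for RR, the reciprocal of rate. Both points have force. A reader might infer that the plan as a whole is blind to heart-rate bias, and the documents do not support that. They equally do not say that the plots extend to the 30-second mean heart rate: the sentence closes a paragraph on calliper intervals, and its purpose clause uses the vocabulary of outcome 2.

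A second reply is that r is not worthless, and this is also right. It falls as random error grows: with SD_HR 20, r is 0.97 for SD_err 5, 0.89 for SD_err 10 and 20/√(400 + 225) = 0.80 for SD_err 15. It is therefore too strong to infer that almost any device would exceed 0.95, or that the two devices could not be told apart. The weakness is specific to systematic error and to dependence on the sample's spread.

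Third, the plan sets no value of r at which a device would be called accurate, so a false declaration of accuracy is not built in. Nothing in the documents suggests that either device has a 10 bpm offset.

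Finally, this is one of four secondary outcomes, and the tracings are stored, so bias and limits can still be computed from the same recordings. That limits the harm, but the listed outcome still does not match its objective.

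**Conclusion.** The point stands in a limited form. The one outcome listed for secondary objective 3 cannot answer a question about accuracy, because constant error leaves r unchanged and proportional error leaves it nearly so. Under the assumed SD_HR of 20 bpm and SD_err of 5 bpm, r is 0.97 for a bias of 0 or of 10 bpm, while the limits of agreement move from ±9.8 bpm to 0.2 to 19.8 bpm. For SD_HR of 15 to 25 bpm, r is 0.95 to 0.98; larger random error lowers it. The algebra does not depend on these values, but the size of r does.

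The Section 10 plots are a partial safeguard: they would reveal a gross rate error carried in the tracing, but they are not tied to the 30-second mean rate and rest on three beats. The documents support no wider conclusion about the plan's ability to detect bias or about how either device will perform. The primary objective is unaffected.

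**What to change.** In Sections 3 and 6, make outcome 3 the mean difference (device minus simultaneous 12-lead) in 30-second mean heart rate with 95% limits of agreement, each with a 95% CI, reported separately for each device. Keep the correlation coefficient as a descriptive statistic only. In Section 10, extend the agreement sentence so that it explicitly names mean heart rate as well as the intervals, and state whether the mean rate is device-reported or read from the trace.

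Two additions are optional: a split by AF status, and the percentage of recordings within a margin fixed before analysis.

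The cost is a change of wording in three sections and one more table. The recordings and the sample size stay the same, and nothing is added for participants.

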## 7. STUDY DESIGN

This study is a prospective, multicentre, observational study comparing rhythm and heart rate detection of two novel wearable devices — the Skylab CART-I ring and Apple Watch Series 6 — to a 12-lead ECG (gold-standard) for different cardiac rhythm disorders. We will recruit 500 participants attending Cardiology outpatient appointments, procedures or investigations (including the catheterisation laboratory) and inpatients in the cardiology and cardiothoracic wards in three hospitals across the UK. All patients will be due a 12-lead ECG as part of their standard of care.

If participants agree to take part in this study, the research team will provide them with instructions and will demonstrate how to use the wearable devices. Participants will then be asked to perform a simultaneous 30-seconds 12-lead ECG and 1-lead ECG for each wearable device (Skylab CART-I ring or Apple Watch). The order of recordings will be randomly assigned. If the first recording is uninterpretable due to artefact, a second recording will be allowed.

[figure not shown]
The SkyLabs CART-I Ring generates a 30-second 1-lead ECG by placing the participants finger on the rings' metal casing. Similarly, the Apple Watch 1-lead ECG requires the participant to place his/her finger on the metal crown. The 1-lead ECGs will be displayed and saved in the CART-I ring app and Apple Health app of a research iPhone SE, respectively. The smartphone apps will not contain any identifiable data and participants will only be identified by the time stamp of their recordings. The clocks of the Apple Watch, SkyLabs CART-I ring and ECG machine will be synchronised. The 12-lead ECG will also contain a time stamp and the study ID number (site code and participant number), it will then be recorded by using the iPhone SE camera and exported in PDF format for subsequent analysis. The 12-lead ECGs time stamp will also be documented in the CRF. The 12-lead ECGs will be added to the participants medical notes and available to the clinical team. The 1-lead ECGs from the wearable devices will only be available to the research team.

This study does not involve any follow-up visits. All the 1-lead ECGs stored in the CART-I Ring app and Apple Health app will be exported in PDF format. All ECGs (12-lead ECGs and 1-lead ECGs from the wearable devices) will be analysed by two Cardiologists (based at Oxford University Hospital NHS Foundation Trust/OUHFT) blinded to patient's data. Any disagreement will be resolved by a third Cardiologist (CI of the study).

